8.2.3 Adverse events of focus

Rozanolixizumab adverse events of focus (AEOF) include the following categories:

- Headaches
- Gastrointestinal disturbances
- Hypersensitivity reactions
- Anaphylactic reactions
- Injection site reaction
- Infusion reaction
- Infections
- Opportunistic infections
- Reductions in albumin and plasma proteins
- Effects on the kidney
- Drug related hepatic disorders
- Effects on lipids

1. The number and percentage of study participants who experience each category of the AEOF will be summarized by most recent dose level prior to onset of the AEOF and RLZ total treatment group. The following summaries will be presented by SOC, HLT, and PT:

- AEOF
- Serious AEOF
- AEOF by relationship
- AEOF by maximum intensity (mild, moderate and severe)

2. Additionally, the summaries for the AEOF headache and gastrointestinal disturbances in Treatment Period by intensity will be presented separately by most recent dose level and RLZ total.

3. Graphs for AEOF headache in Treatment Period by time of onset (relative to infusion), severity, causality and duration for each study participant will also be provided.

A by-subject listing of all AEOF by category (as listed above) will be provided by treatment group and participant. Most recent dose will be presented in listing even when the AE start date is partial. Further details related to the statistical analysis of the above mentioned treatment-emergent AEOFs are provided in [Section 13.8](#).

8.3 Clinical safety laboratory assessments

The following table ([Table 8-1](#)) lists safety laboratory assessments that are collected throughout the study:

Table 8-1: Clinical Laboratory Parameters

Laboratory Assessments	Parameters			
Hematology	Platelet Count	RBC Indices:		White Blood Cell (WBC) Count with Absolute Count and Differential: Neutrophils Lymphocytes Monocytes Eosinophils Basophils
	Red Blood Cell (RBC) Count	Mean corpuscular volume		
	Hemoglobin	Mean corpuscular hemoglobin		
	Hematocrit	%Reticulocytes		
Clinical Chemistry	Blood Urea Nitrogen (BUN)	Potassium	Aspartate Aminotransferase (AST) / Serum Glutamic-Oxaloacetic Transaminase (SGOT)	Total and direct bilirubin
	Estimated Glomerular Filtration Rate (eGFR) ^a	Sodium	Alanine Aminotransferase (ALT) / Serum Glutamic-Pyruvic Transaminase (SGPT)	Total Protein
	Glucose (fasting)	Calcium	Alkaline phosphatase (ALP)	Creatinine
	Lactate dehydrogenase (LDH)	C-reactive protein	Albumin	
Routine Urinalysis	
 • Specific gravity • Albumin, albumin/creatinine, creatinine • pH, glucose, protein, ketones, bilirubin, urobilinogen, nitrite, leukocyte esterase, hemoglobin by dipstick • Microscopic examination (if blood or protein is abnormal) 			
Other Screening Tests	
 • Urine human chorionic gonadotropin (hCG) pregnancy test (as needed for women of childbearing potential)^b • Serology testing for HIV, hepatitis B, and hepatitis C • Partial Prothrombin Time (PTT), and International Normalized Ratio (INR), and Hemoglobin A1C (HbA1c) tests 			

NOTES:
 
All study-required laboratory assessments will be performed by a central laboratory. The results of each test must be entered into the CRF.
				

Laboratory Assessments	Parameters

^a eGFR is calculated using the Chronic Kidney Disease Epidemiology Collaboration (CKD-EPI) formula which is $eGFR = 141 * \min(Scr/\kappa, 1)^\alpha * \max(Scr/\kappa, 1)^{-1.209} * 0.993^{Age} * 1.018$ [if female] * 1.159 [if black]; where Scr is serum creatinine (mg/dL), κ is 0.7 for females and 0.9 for males, α is -0.329 for females and -0.411 for males, min indicates the minimum of Scr/κ or 1, and max indicates the maximum of Scr/κ or 1. If race is not captured, participant will be assumed not Black in the calculation.
 
^b Local urine testing will be standard for the protocol unless serum testing is required by local regulation or Institutional Review Board (IRB)/ Independent Ethics Committee (IEC).
	

Chemistry, hematology and quantitative urinalysis (observed value, absolute change from Baseline) will be summarized in standard unit using descriptive statistics by most recent dose received and RLZ total at each scheduled visit.

The central lab data will be used for the summary tables. Repeated lab measurements will be handled per [Section 4.3](#).

Measurements below the lower limit of quantification (BLQ) will be imputed with half of the lower limit of quantification (LLOQ), and measurements above the upper limit of quantification (ALQ) will be imputed to the upper quantification limit for the purpose of quantitative summaries.

The number and percentage of participants who meet each of the markedly abnormal (MA) criteria outlined in [Section 13.7](#) will be summarized by most recent dose received at any visit (including unscheduled visit).

The laboratory variables that are categorized as normal, high or low based on the reference range supplied by the analytical laboratory will be presented in shift tables from Baseline to any post-Baseline visit (including unscheduled visit) by most recent dose received.

All central or local laboratory test results will be listed, including Baseline, scheduled and unscheduled visits with results in standard unit. Values outside the reference range for the continuous variables will be flagged in the listings. The reference ranges will also be reported in the listings. In addition, the listings will include a flag for values identified as MA. Additional lab test, including pregnancy testing, will also be listed.

8.3.1 Potential drug-induced liver injury

The number and percentage of study participants who meet one or more of the following potential drug-induced liver injury (pDILI) criteria will be summarized by treatment group and RLZ total:

- Participants with at least one post-Baseline liver laboratory assessment
- Incidence of potential hepatotoxicity with symptoms potentially associated with hepatitis or hypersensitivity
- Incidence of potential hepatotoxicity with no symptoms potentially associated with hepatitis or hypersensitivity

- Laboratory criteria for pDILI:
 - (AST or ALT > 3 x ULN) and TBL > 1.5 x ULN
 - (AST or ALT > 3 x ULN) and TBL > 2 x ULN
 - (AST or ALT > 3 x ULN) and TBL > 2 x ULN and ALP < 2 x ULN (Hy's Law)

In order to meet the above criteria, a study participant must experience the elevation in bilirubin and ALT or AST (and the absence of the ALP elevation) at the same visit. For example, a study participant who experiences a >2xULN elevation of bilirubin at one visit and a >3xULN elevation in ALT (or AST) at a subsequent visit has not fulfilled the Hy's law criteria. If participant has one value unknown, then he/she should not be considered for meeting the above criteria.

Additional analyses for liver function tests (LFTs) will be performed to assess the potential for liver toxicities in accordance with the United States Food and Drug Administration guidelines. Per guidelines, the following criteria will be used to define levels of LFT elevation:

- Aspartate aminotransferase (AST): >3 x ULN, >5 x ULN, >8 x ULN, >10 x ULN, >20 x ULN
- Alanine aminotransferase (ALT): >3 x ULN, >5 x ULN, >8 x ULN, >10 x ULN, >20 x ULN
- AST or ALT: >3 x ULN, >5 x ULN, >8 x ULN, >10 x ULN, >20 x ULN
- Total bilirubin (TBL): >1.5 x ULN, >2 x ULN
- Alkaline phosphatase (ALP) >1.5 x ULN

A listing will also be provided for study participants who meet at least one of the above criteria. All results obtained at that visit for the specified parameters will be displayed.

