8.3.6 Adverse events of special interest

An AE of special interest (AESI) is any AE that a regulatory authority has mandated be reported on an expedited basis, regardless of the seriousness, expectedness, or relatedness of the AE to the administration of a UCB product/compound. An AESI should be reported within 24 hours.

Potential Hy's Law, defined as $\geq 3 \times \text{ULN}$ ALT and $\geq 2 \times \text{ULN}$ bilirubin ($>35\%$ direct bilirubin) or ALT $\geq 3 \times \text{ULN}$ and international normalized ratio (INR) >1.5 , if INR measured, with no alternative explanation for the biochemical abnormality, must ALWAYS be reported to UCB as an AESI (ie, without waiting for any additional etiologic investigations to have been concluded). Follow-up information should then be reported if an alternative etiology is identified during investigation and monitoring of the participant.

All AESIs will follow the AE recording and reporting procedures as indicated in Appendix 3 (Section 10.3).

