10.6 Appendix 6: Liver Safety – Suggested Actions and Follow-up Assessments

Participants with PDILI must be assessed to determine if study medication must be discontinued. In addition, all concomitant medications and herbal supplements that are not medically necessary should also be discontinued.

Investigators should attempt to obtain information on study participants in the case of study medication discontinuation to complete the final evaluation.

Study participants with PDILI should not be withdrawn from the study until investigation and monitoring are complete. All results of these evaluations and observations, as well as the reason(s) for study medication discontinuation and/or participant withdrawal (if applicable), must be recorded in the source documents. The eCRF must document the primary reason for discontinuation of study medication.

A specific monitoring plan must be agreed between the UCB study physician and the Investigator for study participants who have ALT >5xULN. The monitoring plan should include any necessary follow-up assessments (until resolution of the abnormal lab values).

Phase 3 liver chemistry stopping criteria are designed to assure participant safety and to evaluate liver event etiology. Stopping criteria are presented in [Table 10-2](#) and increased monitoring criteria are presented in [Table 10-3](#).

Table 10-2: Phase 3 liver chemistry stopping criteria and follow-up assessments

Liver Chemistry Stopping Criteria	
ALT-absolute	ALT ≥8xULN
ALT increase	ALT ≥5xULN but <8xULN persists for ≥2 weeks ALT ≥3xULN but <5xULN persists for ≥4 weeks
Bilirubin^{a, b}	ALT ≥3xULN and bilirubin ≥2xULN (>35% direct bilirubin)
INR^b	ALT ≥3xULN and INR >1.5, if INR measured
Cannot mMonitor	ALT ≥5xULN but <8xULN and cannot be monitored weekly for ≥2 weeks ALT ≥3xULN but <5xULN and cannot be monitored weekly for ≥4 weeks
Symptomatic^c	ALT ≥3xULN associated with symptoms (new or worsening) believed to be related to liver injury or hypersensitivity
Suggested Actions and Follow-up Assessments	
Actions	Follow-up Assessments

This document cannot be used to support any marketing authorization application and any extensions or variations thereof.

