8.2.2 Adverse events summaries

TEAEs will be summarized by the most recent dose level prior to onset of TEAEs and RLZ total, including the number and percentage of study participants and frequency. Additional details are described below:

1. Overview of TEAEs will include following categories: any TEAEs, serious TEAEs, participant discontinuation due to TEAEs, permanent withdrawal of IMP due to TEAEs,

temporary withdrawal of IMP due to TEAEs, TEAEs requiring dose change, treatment-related TEAEs, severe TEAEs, TEAEs leading to death, all deaths (AEs leading to death).

2. Incidence of TEAEs will be summarized by SOC, HLT, PT for:

- Any TEAEs
- Any TEAEs during Treatment Period
- Any TEAEs by maximum intensity (mild, moderate and severe)
- Any TEAEs by relationship
- Severe TEAEs
- Non-serious TEAEs above reporting threshold of 5% of study participants
- Fatal TEAEs
- Fatal TEAEs by relationship
- Serious TEAEs
- Serious TEAEs by relationship
- Participant discontinuation due to TEAEs
- TEAEs leading to permanent withdrawal of IMP
- TEAEs leading to temporary withdrawal of IMP
- TEAEs requiring dose change
- Treatment-emergent AESM
- Treatment-emergent AESI

3. Incidence of any TEAEs will be summarized by decreasing frequency of PT.

AESMs include severe headache, severe GI disorders (i.e., abdominal pain, diarrhea, vomiting), and opportunistic infection.

AESIs are the cases of potential Hy's Law (see [Section 8.3.1](#)).

AESMs and AESIs will be identified based on the assessment by the Investigator as recorded in the CRF. An AE will be counted as an AESM if there is a 'yes' response to the question "Adverse event of Special Monitoring?" and 'no' otherwise. An AE will be counted as an AESI if there is a 'yes' response to the question "Adverse Event of Special Interest?" and 'no' otherwise.

When applicable adverse event summaries will be ordered by alphabetical SOC, alphabetical HLT within SOC and decreasing frequency of PT in the RLZ total column for tables.

Listings of all TEAEs, all non-serious TEAEs, serious TEAEs, permanent withdrawal of IMP due to AEs, study participant discontinuation from study due to AEs, AEs leading to death, AESIs, AESMs will be presented by treatment group and participant. Persistent AEs and TEAE will be flagged in the listings. Most recent dose will be presented in listing even when the AE start date is partial.

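### The SAP's Hy's Law row is not the protocol's potential Hy's Law, so some qualifying cases can score zero in every combined liver-injury row

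*SAP*

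**What the plan says.** **Protocol.** Section 8.3.6 defines potential Hy's Law by two routes, both starting from ALT at or above 3xULN. Table 10-2 (Appendix 6) uses the same thresholds as stopping criteria: "ALT ≥3xULN and bilirubin ≥2xULN (>35% direct bilirubin" for bilirubin and "ALT ≥3xULN and INR >1.5, if INR measured" for INR. Section 8.3.6 adds a clinical condition and a reporting duty: "if INR measured, with no alternative explanation for the biochemical abnormality, must ALWAYS be reported to UCB as an AESI". Footnote b of Table 10-2 does not apply the INR threshold to participants on anticoagulants. Neither definition contains an ALP condition, and neither says whether the two abnormal values must come from one visit.

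**SAP.** Section 8.3.1 combines AST or ALT above 3xULN with total bilirubin (TBL) above 1.5xULN, then with TBL above 2xULN, and lastly gives "AST or ALT > 3 x ULN) and TBL > 2 x ULN and ALP < 2 x ULN (Hy's Law". It requires that "a study participant must experience the elevation in bilirubin and ALT or AST (and the absence of the ALP elevation) at the same visit", and its example rejects bilirubin and ALT rises seen at successive visits. It closes with: "If participant has one value unknown, then he/she should not be considered for meeting the above criteria". No row uses INR, although SAP Table 8-1 lists INR among the tests. SAP 8.2.2 says "AESIs are the cases of potential" Hy's Law, cross-refers to 8.3.1, and then takes the AESI count from the Investigator's CRF answer. SAP 3.9, which records departures from protocol-defined analyses, does not mention the different definition.

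**The concern.** One term carries two definitions. The Investigator decides whether to tick AESI under Protocol 8.3.6. The laboratory table, which should be the independent check on that tick, applies other rules under the same name. A participant can therefore be an AESI for potential Hy's Law while the laboratory Hy's Law count reads 0, and no reconciliation is planned.

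Long-term safety is the primary objective, and potential Hy's Law is a finding for which a single case matters. A reader who goes straight to the row with that label may take its zero to mean that nobody met the protocol's thresholds.

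**Working it through.** The documents give no figure on this point, so there is none to reproduce. The check applies both rule sets to constructed laboratory profiles.

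**Rules (multiples of ULN, except INR)**
- Protocol 8.3.6 and Table 10-2, laboratory part: ALT ≥3 and [(bilirubin ≥2 and direct >35%) or INR >1.5].
- SAP 8.3.1: max(ALT, AST) >3 and, in turn, TBL >1.5; TBL >2; TBL >2 with ALP <2. All values must come from one visit. On a literal reading, none of ALT, AST, TBL or ALP may be unknown.

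**Profiles.** Direct bilirubin is set at 50% throughout. Unless stated, ALT, AST and ALP are 1x, TBL is 0.8x, and INR is not measured.

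| Profile | Protocol thresholds | SAP TBL >1.5x | SAP TBL >2x | SAP Hy's Law |
|---|---|---|---|---|
| 1. ALT 4x, TBL 2.5x | met | 1 | 1 | 1 |
| 2. ALT 4x, TBL 1.2x, INR 1.8 | met | 0 | 0 | 0 |
| 3. ALT 4x at one visit; TBL 2.5x with ALT 2.5x at the next | met only if no timing limit is read in | 0 | 0 | 0 |
| 4. ALT 4x, TBL 2.5x, ALP unknown | met | 0 | 0 | 0 |
| 5. ALT 4x, TBL 2.5x, ALP 2.5x | met | 1 | 1 | 0 |
| 6. ALT exactly 3x, AST 2.9x, TBL 2.5x | met | 0 | 0 | 0 |
| 7. ALT 4x, TBL exactly 2x | met | 1 | 0 | 0 |

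Profiles 2, 4, 5, 6 and 7 meet the protocol thresholds at a single visit and score 0 in the SAP's Hy's Law row. Profiles 2, 4 and 6 score 0 in all three combined rows. None of these five needs an argument about timing.

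**Where the three zeros still show.** In the single-analyte rows of 8.3.1, profile 2 is counted under ALT >3xULN, profile 4 under ALT >3xULN and TBL >2xULN, and profile 6 under TBL >2xULN only. If the unknown-value rule covers only the analytes a row uses, profile 4 becomes 1, 1, 0.

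**Size of one missed case (illustration).** Take N = 240, the maximum in SAP 3.9, with exact 95% limits. For 0/240 the upper limit is 1 − 0.025^(1/240) = 1.5%. For 1/240 the estimate is 0.4%, with lower limit 1 − 0.975^(1/240) = 0.01% and exact upper limit 2.3%.

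**The case against.** **The zero is confined to three rows.** SAP 8.3.1 also tabulates ALT, AST, TBL and ALP separately and lists anyone meeting a criterion. Potential Hy's Law is also counted in the AESI table if ticked, and Table 10-2 footnote b requires it to be reported as an SAE. This stands: the cases need not vanish from the report. However, the 8.3.1 listing shows only the specified parameters at the qualifying visit, and INR is not among them.

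**The full protocol definition needs clinical judgement.** Another cause must be ruled out, so the Investigator's answer is a proper source. This stands, and any added laboratory row must be labelled as preceding that assessment. It does not justify giving the same name to a different laboratory rule.

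**The SAP is also broader.** It accepts AST, does not require direct bilirubin above 35%, and does not exclude other causes. This stands: the two counts can differ in either direction.

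**The awkward cases may be few.** INR is scheduled only at Visit 1, Week 52 or PEOT, and EOS; otherwise it is event-driven. ALP belongs to the required repeat panel, so ALP missing alone should be uncommon. The unknown-value sentence could also be meant criterion by criterion. All of this bears on frequency; the written rule still says something else.

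**A stronger inference the documents do not support.** A reader might conclude that, with chemistry 28 days apart from Week 9 to Week 49, the same-visit rule misses most cases in which bilirubin lags ALT. Assume ALT is raised on days 0 to 21 and bilirubin from day 7 or day 14; the documents give no durations. The scheduled grid alone then hits the overlap with probability 14/28 = 0.50 or 7/28 = 0.25, against 21/28 = 0.75 for seeing the ALT rise. But Appendix 6 requires weekly liver chemistry once ALT reaches 3xULN. If ALT is first seen on day t, one of t, t+7 and t+14 falls in days 14 to 21, when both are raised. The same-visit probability is then also 0.75 and nothing is lost, provided follow-up samples count. Nor does the same-visit rule contradict the protocol, which is silent on timing.

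**Conclusion.** The point holds as a mismatch of definitions that can give a misleading count in a labelled safety row. The INR route, the ≥ signs and the ALP condition follow directly from the two texts. The unknown-ALP case rests on reading that sentence literally. The same-visit rule is an added restriction, not a conflict.

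The number of participants affected cannot be estimated from the documents and may be none. The practical size is one or a few cases placed in the wrong row, with a laboratory count that disagrees with the AESI count and no plan to explain it. A reader might infer that liver cases would go unreported altogether; the single-analyte rows, listings, and AESI and SAE tables rule that out. It is worth correcting because the change is small and safety is the primary objective.

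One gap remains open. SAP 8.3 says its marked-abnormality and shift tables include unscheduled visits, while 8.3.1 is silent. The reassurance about lagged rises depends on those samples counting.

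**What to change.** In SAP 8.3.1, keep the three combined rows and make these changes:

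1. Add one row for the laboratory part of Protocol 8.3.6: ALT ≥3xULN with bilirubin ≥2xULN and direct bilirubin above 35%, or with INR >1.5. Do not apply the INR threshold to participants on anticoagulants (Table 10-2, footnote b). Label the row as laboratory criteria before clinical assessment of other causes.
2. State that unscheduled and follow-up samples count. Allow the INR taken at the follow-up required by Table 10-2 to pair with the triggering ALT. Because SAP 8.3 bases summary tables on central laboratory data, say also whether local follow-up results are used.
3. Limit the unknown-value rule to the analytes each row uses.

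In SAP 8.2.2, point the AESI sentence to Protocol 8.3.6, and list any participant for whom the AESI and laboratory counts disagree. Record the remaining difference between the SAP's Hy's Law row and the protocol definition in SAP 3.9.

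A further row pairing ALT with later bilirubin inside a stated window is optional, since the protocol sets no timing. The cost is SAP wording, one added row and a short discordance listing, with no new data and no change to clinical management. The downside is a little more tabulation and possibly a slightly higher count of potential cases.

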8.4 Vital signs, physical findings, and other observations related to safety

8.4.1 Vital signs

Observed values and changes from Baseline will be summarized by vital signs variable (pulse rate, systolic and diastolic blood pressure, and temperature), scheduled visit, most recent dose received and RLZ total.

The number and percentage of participants who meet each of the MA criteria outlined in [Section 13.7](#) will be summarized by most recent dose received and RLZ total at any visit (including unscheduled visit).

Additionally, the vital signs variables that are categorized as normal or MA based on the MA criteria will be presented in shift tables from Baseline to any post-Baseline visit (including unscheduled visit) by most recent dose received.

A by-participant listing of all vital sign measurements and change from Baseline will be presented by treatment group and visit. The listing will include a flag for values identified as MA. Unscheduled measurements will be presented in the listings.

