13.7 Markedly abnormal laboratory and diagnostic criteria for Rozanolixizumab program

The following criteria will be applied in the determination of marked abnormalities for laboratory assessment values. They are based on Version 5 of the Common Terminology Criteria for Adverse Events (CTCAE) grade 3 or higher criteria unless otherwise noted. If both high and low criteria are shown for a parameter, the criteria should be summarized separately in tabular or graphical data summaries.

Table 13-10: Hematology

Parameter	Unit (conventional)	Unit (standard)	Marked Abnormality Criteria
Hemoglobin	g/dL	g/L	<8.0 g/dL, <80 g/L
WBC (Leukocytes) ¹	10 ⁹ /L	10 ⁹ /L	Low: <2.0 x 10 ⁹ /L High: >30 x 10 ⁹ /L
Lymphocytes Absolute	10 ⁹ /L	10 ⁹ /L	Low: <0.5 x 10 ⁹ /L High: >20 x 10 ⁹ /L
Neutrophils Absolute	10 ⁹ /L	10 ⁹ /L	<1.0 x 10 ⁹ /L
Platelets	10 ⁹ /L	10 ⁹ /L	<50.0 x 10 ⁹ /L

¹WBC (Leukocytes) markedly abnormal high criterion is not based on Version 5 CTCAE Grade 3 or higher criteria. Due to the mechanism of action of RLZ, the safety alert is related to infection risk which would be identified by a lower cut-point than the standard which is related to acute leukemias. A markedly abnormal high cut-point >30 x 10⁹/L is applied to flag leukocytosis (George 2012).

Table 13-11: Chemistry

Parameter	Unit (conventional)	Unit (standard)	Marked Abnormality Criteria
AST (SGOT)	U/L	U/L	>5.0 x ULN
ALT (SGPT)	U/L	U/L	>5.0 x ULN
ALP (Alkaline Phosphatase)	U/L	U/L	>5.0 x ULN
GGT (Gamma Glutamyl Transferase)	U/L	U/L	>5.0 x ULN
Bilirubin (Total)	mg/dL	umol/L	>3.0 x ULN if Baseline value is normal; >3.0 x Baseline value if Baseline is abnormal
Albumin	g/dL	g/L	<2 g/dL; <20 g/L
Creatinine	mg/dL	umol/L	>3.0 x ULN
Estimate glomerular filtrate rate (eGFR) ¹	mL/min/1.73 m ²	mL/min/1.73 m ²	eGFR <29 mL/min/1.73 m ²

C reactive protein (CRP) ²	mg/L	mg/L	>10 mg/L
Calcium ³	mg/dL	mmol/L	Low: Corrected serum calcium of <7.0 mg/dL; <1.75 mmol/L
			High: Corrected serum calcium of >12.5 mg/dL; >3.1 mmol/L
Immunoglobulin G ⁴	(g/L)	(g/L)	≤1 g/L
Potassium	mmol/L	mmol/L	Low: <2.5 mmol/L
			High: >6.0 mmol/L
Sodium	mmol/L	mmol/L	Low: <125 mmol/L
			High: >155 mmol/L
Glucose ⁵	mg/dL	mmol/L	Low: <40 mg/dL; <2.2 mmol/L
			High: >250 mg/dL; >13.9 mmol/L
Total Cholesterol	mg/dL	mmol/L	>400 /dl; >10.34 mmol/L
Triglycerides	mg/dL	mmol/L	>500 mg/dl; >5.7 mmol/L

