Abbreviations: ALT= alanine aminotransferase; AST = aspartate aminotransferase; dL = deciliter; GGT: gamma-glutamyltransferase; L = liter; mg = milligram; mmol = millimoles; µg = microgram; U = unit; ULN = upper limit of normal

Note: Marked abnormality criteria are defined by Grade 3 or higher events according to the Common Terminology for Adverse Events (CTCAE), Version 5.0, November 17, 2017 unless otherwise noted.

¹eGFR is calculated using the Chronic Kidney Disease Epidemiology Collaboration or CKD-EPI formula (https://qxmd.com/calculate/calculator_251/egfr-using-ckd-epi) which is $eGFR = 141 * \min(\text{Scr}/\kappa, 1)^\alpha * \max(\text{Scr}/\kappa, 1)^{-1.209} * 0.993^{\text{Age}} * 1.018$ [if female] * 1.159 [if black]; where Scr is serum creatinine (mg/dL), κ is 0.7 for females and 0.9 for males, α is -0.329 for females and -0.411 for males, min indicates the minimum of Scr/ κ or 1, and max indicates the maximum of Scr/ κ or 1. For derivation from values in standard units (umol/L) the κ values are 61.88 for females and 79.56 for males.

²Includes CRP and High Sensitivity (HS) CRP. Reference for marked abnormality criteria: Nehring, S.M.; Goyal, A.; Patel, B.C. (2020). StatPearls Publishing. web link: <https://www.ncbi.nlm.nih.gov/books/NBK441843/>.

³Corrected Calcium (mmol/L) = 0.02 * (40 – Albumin (g/L)) + Calcium (mmol/L).

⁴Immunoglobulin G criterion based on immunodeficiency literature and noted in RLZ study protocols.

⁵Glucose high criterion defined by Grade 3 and higher events according to CTCAE, Version 4.03, June 14, 2010.

Table 13-12: Vital Signs

Parameter	Abnormality Criteria
Pulse Rate (beats/minute)	≤50 and a decrease from Baseline of ≥15 ≥120 and an increase from Baseline of ≥15
Systolic Blood Pressure (mmHg)	≤ 90 and a decrease from Baseline of ≥20 ≥ 180 and an increase from Baseline of ≥20
Diastolic Blood Pressure (mmHg)	≤50 and a decrease from Baseline of ≥15 ≥105 and an increase from Baseline of ≥ 15
Temperature	>101 °F (38.3 °C)

Parameter	Abnormality Criteria
Body Weight	$\geq 10\%$ decrease from Baseline $\geq 10\%$ increase from Baseline

Table 13-13: Electrocardiogram

Parameter	Abnormality Criteria
QT interval (ms)	≥ 500 ms
	≥ 60 ms increase from Baseline
QTc(F) (ms)	≥ 500 ms
	≥ 60 ms increase from Baseline
PR interval (ms)	Treatment-emergent value >200 ms
QRS interval (ms)	Treatment-emergent value >100 ms
Heart rate (bpm)	<50 bpm
	>120 bpm

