Abbreviations: bpm = beats per minute; ms = milliseconds; QTc(F) = Fridericia corrected QT interval;
 Note: Treatment-emergent is defined as meeting the criteria at any post-Baseline visit after the first infusion of study medication and within 56-days of the last infusion and not meeting the same criteria during Baseline

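### For pulse and blood pressure, the normal/MA shift table cannot show a markedly abnormal Baseline; absolute laboratory and ECG MA counts also ignore Baseline status

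*SAP*

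**What the plan says.** **Vital signs.** SAP 8.4.1 summarizes four variables: "pulse rate, systolic and diastolic blood pressure, and temperature". It plans an incidence table of participants meeting each MA criterion, and then states that "the vital signs variables that are categorized as normal or MA based on the MA criteria will be presented in shift tables from Baseline"; the comparison is with any visit after Baseline. The criteria are in SAP 13.7, Table 13-12. Low pulse is "≤50 and a decrease from Baseline of ≥15", and low diastolic pressure has the same form. High systolic pressure is "≥ 180 and an increase from Baseline of ≥20". The remaining pulse and blood-pressure criteria are built the same way. Temperature has an absolute limit only (above 38.3 °C).

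**Laboratory.** SAP 8.3 says that participants meeting each MA criterion "will be summarized by most recent dose received at any visit (including unscheduled visit". Nearly all limits in Tables 13-10 and 13-11 are absolute. Total bilirubin is the exception, with the alternative limit ">3.0 x Baseline value if Baseline is abnormal". A separate shift table covers laboratory variables "categorized as normal, high or low based on the reference range supplied by the analytical laboratory will be presented in shift tables from Baseline", so it uses reference ranges and not the MA limits.

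**ECG.** SAP 8.4.2 counts MA at any visit in the same way. In Table 13-13 only PR and QRS must be treatment-emergent, which the table note defines as met after the first infusion "and within 56-days of the last infusion and not meeting the same criteria during Baseline".

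**The concern.** A shift table exists to separate participants who were already abnormal at entry from those who became so on drug. If the definition of abnormal includes a change from Baseline, the entry category cannot be populated. The table then appears to show that everyone started normal, although it never tested this. Pulse and systolic and diastolic pressure are the vital signs named as safety endpoints in SAP 2.2.1.2, and Protocol 5.1 and 5.2 set no numeric entry limit for any of them. Extreme entry values are therefore possible.

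The laboratory and ECG counts have a different weakness. Under an absolute limit, a participant who is beyond it before the first MG0004 dose and stays there is counted as an MA case under whichever dose was most recent. After a dose switch the same participant can be counted under both doses. Protocol Table 6-2 permits oral corticosteroids without a dose requirement, and no numeric entry limit applies to glucose, lymphocytes or CRP, so MA values at entry are plausible for some parameters.

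**Working it through.** The documents give no figure on this point to reproduce. The check applies the stated criteria to a Baseline value.

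**1. Can a Baseline value be MA?** The inputs are from SAP Table 13-12. Change from Baseline at Baseline = value − the same value = 0.

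| Variable | Absolute limits | Change also required | Change at Baseline | MA at Baseline possible? |
|---|---|---|---|---|
| Pulse (beats/min) | ≤50 or ≥120 | ≥15 | 0 | No |
| Systolic (mmHg) | ≤90 or ≥180 | ≥20 | 0 | No |
| Diastolic (mmHg) | ≤50 or ≥105 | ≥15 | 0 | No |
| Temperature | >38.3 °C | none | not used | Yes |

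Evaluating the criteria with each value as its own Baseline, over pulse 30 to 200, systolic 60 to 260 and diastolic 30 to 160, returns no MA value. For temperature, values above the limit are MA.

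**2. What the shift table then contains.** Take N participants with Baseline and post-Baseline values, of whom m are MA post-Baseline. For pulse and both pressures:

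- MA to normal = 0 and MA to MA = 0
- normal to MA = m
- normal to normal = N − m

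The only free number is m, which the incidence table already reports.

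**3. Examples.**

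- Systolic 185 at Baseline and 190 later: change 190 − 185 = 5, below 20, so normal to normal. This participant becomes MA only at 185 + 20 = 205.
- Systolic 185 at Baseline, later below 180: also normal to normal, so the improvement is not shown either.
- Pulse 48 at Baseline and 46 later: a fall of 2, below 15, so normal to normal.

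**4. How many laboratory criteria are exposed?** High and low limits are counted separately in Tables 13-10 and 13-11.

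- Total criteria: 27. Absolute: 26.
- Bilirubin is relative to Baseline and cannot be met there. A normal Baseline is not above 3 × ULN, and an abnormal one is not above 3 times itself.
- GGT, total cholesterol and triglycerides are not among the parameters in SAP Table 8-1: 26 − 3 = 23.
- Protocol 5.2 should exclude Baseline MA for neutrophils, ALT, AST, ALP and GFR: 23 − 5 = 18.

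So at most 18 absolute criteria can plausibly be met at Baseline, including CRP, glucose, lymphocytes and potassium. Exclusion 9 (investigator-judged significant laboratory abnormality) may remove some cases. In the other direction, eligibility may rest on a lead-in value up to 32 days old, so the entry limits are not a complete guard.

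**5. ECG.** Of 8 criteria in Table 13-13, 2 are changes from Baseline (QT and QTcF, 60 ms), 2 are treatment-emergent (PR, QRS) and 4 are absolute (QT and QTcF at 500 ms, heart rate below 50 and above 120). Exclusion 18 caps QTc at 480 ms or lower, so QTcF of 500 ms at Baseline should be rare. Uncorrected QT and heart rate have no numeric entry limit.

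**6. Size of the laboratory effect.** If a share b is MA at Baseline and all of these stay MA, and a share n of the rest become MA, the reported rate is b + (1 − b)n. Neither b nor n is in the documents. Assuming n = 5%:

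- b = 1%: 0.01 + 0.99 × 0.05 = 5.95%
- b = 5%: 0.05 + 0.95 × 0.05 = 9.75%
- b = 10%: 0.10 + 0.90 × 0.05 = 14.5%

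These figures show only how the count behaves. They are not estimates for this trial.

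**The case against.** A reader might infer that none of the MA outputs separates Baseline from on-drug findings. The documents do not support that. The pulse and blood-pressure incidence table requires a change from Baseline, so it does separate them. Bilirubin is relative to Baseline, the 60 ms QT and QTcF criteria are changes, and PR and QRS are treatment-emergent. Nor does the empty Baseline row extend to temperature.

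A reader might also infer that *at any visit* counts a predose value under a dose. SAP 3.6 groups by the dose received before each visit, and a predose Baseline has no MG0004 dose. A value that is MA only at Baseline therefore has no dose column; the wording is unclear there, but the real issue is the abnormality that persists.

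Other outputs help. SAP 8.3 provides change-from-Baseline summaries, the reference-range shift table and listings that include Baseline and flag MA values. SAP 8.4.1 summarizes vital-sign values and changes directly, which is the declared endpoint. SAP 8.4.2 has a Baseline-to-worst shift table of ECG interpretation. Most laboratory MA limits correspond to CTCAE Grade 3 or higher, so Baseline cases may be few.

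Finally, dropping everyone already MA at Baseline would carry its own cost. Under SAP 3.3, Baseline for these measures is the last value before the first MG0004 dose. Some participants had rozanolixizumab in MG0003, and those who needed rescue could enter before completing its Observation Period. Excluding them could hide abnormalities that arose on drug in the lead-in, and any later worsening.

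All of this stands, and it narrows the point. It does not fill the empty row for three vital signs. A high-to-high entry by reference range does not show whether the participant was already MA, and a listing does not correct a tabulated percentage.

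**Conclusion.** The vital-sign point is a matter of logic and needs no assumption about the data. For pulse, systolic and diastolic pressure, three of the four variables, the Baseline-MA row is 0 by construction, extreme entry values are labelled normal, and the table adds nothing to the MA incidence.

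The secondary point holds for persisting abnormalities under absolute criteria: most of Tables 13-10 and 13-11 (not bilirubin), and QT, QTcF and heart rate in Table 13-13. Its size cannot be determined from the documents. A reader might infer from the middle illustration that laboratory MA rates would roughly double, but that rests on an assumed Baseline share and full persistence, and nothing in the plan supports either.

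Severity is minor. No testing is planned, the underlying values are summarized and listed, and no data are lost.

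**What to change.** **SAP 8.4.1.** For the pulse and blood-pressure shift table, class both Baseline and post-Baseline values by the absolute limits of Table 13-12 only; for systolic pressure the categories would be ≤90, >90 to <180 and ≥180. Keep the combined criterion for the incidence table. Temperature needs no change.

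**SAP 8.3 and 8.4.2.** For the absolute laboratory and ECG criteria, state that MA is counted at post-Baseline visits, and split each count by status at MG0004 Baseline: already MA or newly MA. Keep participants who were already MA in the table, because of possible rozanolixizumab exposure in MG0003.

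The cost is SAP wording and reprogramming of existing tables. No new data are needed.
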